10.5 Drug Accountability

The designated pharmacy staff at the clinical study site will maintain accurate records of receipt and the condition of all study drugs, including dates of receipt. In addition, accurate records will be kept by the pharmacy staff of when and how much study drug is dispensed and used by each patient in the study. Any reason for deviation from the protocol dispensing regimen must also be recorded.

Drug accountability records and inventory will be available for verification by the Sponsor or designee. At the completion of the study, there will be a final reconciliation of all study drugs.

Study drug must not be used for any purpose other than the present study. Remaining study drug will be returned to the Sponsor or its agent or destroyed at the clinical study site according to applicable regulations and only after receipt of written authorisation from the Sponsor.

10.6 Blinding and Procedures for Unblinding the Study

10.6.1 Methods for Ensuring Blinding

The study will be conducted in a double-blind fashion, whereby patients and clinical study site staff are blinded to study drug assignment.

The pharmacy staff or any other dedicated person preparing the investigational products will not be blinded to study drug assignment and will be responsible for the blinding of the study drug. During the study, the randomisation codes will be kept in the site's clinical trials pharmacy, accessible to the pharmacy personnel or any other dedicated person only. Upon completion of the study, after the database lock and after the blind is revealed, the randomisation list will be filed in the Study Master File.

10.6.2 Methods for Unblinding a Patient

Individual randomisation code for each randomised patient will be available from electronic Case Report Form (eCRF). The investigator may request unblinding of a patient's treatment assignment mainly in the case of an emergency, when knowledge of the study treatment is essential for the appropriate clinical management or welfare of the patient.

In the event of an emergency, an unblinding tool will be accessible from patient overview in the eCRF and allow to know for each patient his study drug assignment.

Unblinding should only be considered for the safety of the patient. If unblinding is deemed necessary by the investigator, the investigator or designee can unblind the patient's treatment allocation using a specific function in eCRF. The investigator or designee must note the date, time and reason for unblinding and inform the sponsor of unblinding as soon as practicably possible.

The patient whose treatment has been unblinded will continue in the study.

10.7 Prior and Concomitant Medications/Procedures

Medication taken by the patients on entry to the study or at any time during the study in addition to the investigational product, are regarded as concomitant treatments and must be documented in the appropriate sections of the eCRF.

Parenteral nutrition, vitamin supplements and stool softener will not be recorded in the eCRF.

Relevant previous treatments taken within 24 hours before start of treatment must also be documented in the CRF.

Concomitant medications will be recorded in the eCRF until 3 days after end of infusion (EOI).

Concomitant medications related to AEs (corrective drug required) should be recorded until D28.

Before enrolment into the study, all patients should receive standard of care, including fluid therapy, as recommended in the current version of the guidelines issued by the Surviving Sepsis Campaign (9).

10.7.1 Allowed and Not-Allowed Medications and Procedures

All treatments and procedures required for the treatment of the patient's illness are permitted.

The following concomitant treatments are not permitted during the treatment phase of this study (i.e. study drug infusion):

- Bolus glucocorticoid treatment exceeding 300mg of hydrocortisone or equivalent per day for a maximum of three days

11 STUDY PROCEDURES AND SCHEDULE

An overview on study procedures and schedule is provided in the flowcharts in Figure 1, Figure 2, Figure 3 on pages 21 and 22 and in Table 1 on page 23.

11.1 Obtaining Informed Consent

During screening for eligibility, before any study specific procedure was started, the investigator will obtain informed consent as specified in section 16.2.

11.2 Screening / Pre-treatment Period

The purpose of the screening/ pre-treatment phase is to confirm patient eligibility for enrolment in the study based on the inclusion and exclusion criteria and to obtain written informed consent.

Patients who meet all of the inclusion criteria and none of the exclusion criteria and have provided informed consent can be enrolled in the study.

Note: Before confirming the eligibility of a patient, adequate fluid therapy as recommended in the current guidance of the Surviving Sepsis Campaign (see appendix 1) should be applied.

During the Screening/Pre-treatment period and after obtaining informed consent, the following assessments will be performed:

- Medical history and demographics
- Date of current hospital admission, ICU admission and initiation of invasive mechanical ventilation
- Time and details of fluid and vasopressor therapy
- Previous therapies (within 24 hours prior to screening)
- APACHE II score
- Serum pregnancy test in all female patients
- Physical examination
- Weight and height
- Vital signs
- ECG
- SOFA score
- Blood sample for arterial blood gases (ABG). P/F will be calculated, using equivalence tables for non-ventilated patients
- Clinical laboratory (see Table 2)
- Phone call with the CCC to approve patient inclusion in the study
- Randomisation

11.3 Treatment Period (Days 0 to Day 5)

After meeting all eligibility criteria (confirmed by the CCC, see section 1), eligible patients will be randomised and treatment with MOTREM i.v. will be initiated according to the schedule provided in Table 5 or Table 6.

Note: Treatment with MOTREM must be initiated within 24 hours after the onset of septic shock, defined as the initiation of vasopressor therapy.

11.3.1 Baseline – Treatment Initiation (Day 0)

The following assessments will be performed at baseline before the first administration of study drug:

- Confirmation of patient's eligibility (inclusion exclusion criteria)

- Confirmation of septic shock and time window for treatment initiation (≤ 24 hours after onset)
- Concomitant therapy
- SOFA score
- Vital signs
- ECG
- Vasopressor use
- Invasive mechanical ventilation
- Intubation
- Adverse events
- Blood sample for ABG and P/F
- Blood samples for laboratory tests (according to schedule provided in Table 2):
 - Clinical Laboratory
 - Anti-drug antibodies (ADA)
 - Pharmacokinetics
 - Biomarkers
 - RNA profile
 - Plasma samples for retention
 - Pharmacogenetics (other timepoints are acceptable)
- Initiation of study drug i.v. treatment (according to Table 5 or Table 6)
- Direct antibody test (direct Coombs) before initiation of treatment with study drug

11.3.2 Treatment Period (Day 1 to Day 4)

During the treatment period of up to 5 days, the following assessments will be performed daily (approximately at the same time of day):

- Concomitant therapy
- SOFA score
- Vital signs
- ECG
- Vasopressor use
- Invasive mechanical ventilation
- Intubation
- Mortality
- Adverse events
- Blood sample for ABG and P/F
- Blood samples for laboratory tests (according to schedule provided in Table 2):
 - Clinical Laboratory
 - Pharmacokinetics
 - Biomarkers
 - RNA profile
 - Plasma samples for retention (Day 1 only)
- Continued treatment with MOTREM i.v. (according to Table 5 or Table 6)

11.3.3 End of Infusion/Day 5

Patients will be treated until 12 (± 2) hours after the resolution of their septic shock (defined as vasopressor withdrawal) with a maximum treatment of 5 days (120 (± 2) hours). An

interruption of vasopressor treatment of up to 6 hours is permitted and not considered vasopressor withdrawal).

Patients may also be withdrawn from treatment for other reasons (see section 9.5).

At the end of treatment, the i.v. infusion will be stopped and the following assessments will be performed:

- Concomitant therapy
- SOFA score
- Vital signs
- Weight
- ECG
- Vasopressor use
- Invasive mechanical ventilation
- Intubation
- Mortality
- Adverse events
- Blood sample for ABG and P/F
- Blood samples for laboratory tests (according to schedule provided in Table 2):
 - Clinical Laboratory
 - pharmacokinetics
 - biomarkers
 - RNA profile

If the treatment is stopped any day before D5, the assessments listed above will be performed only once the day of the end of infusion.

For all patients alive, the SOFA score will however be calculated until day 5, no matter when the study treatment stopped. This data will be collected to the extent available in source data and analysed post-hoc (see section 15.5).

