MOTREM PK²	MOTREM circulating levels	Baseline (pre-dose), D1 to D5: daily. EOI PK (if feasible) 15 minutes before EOI and 10 min, 30min and 2h after EOI
Cytokines²	TNF α , IL-6, IL-8, IL-10, CCL2 (MCP-1), IFN γ	Baseline (pre-dose), D1, D3 and D5, FU day 28
Activation of vascular endothelium²	soluble CD62E (E selectin), VEGFR-1, VCAM-1, Ang-1, Ang-2	Baseline (pre-dose), D1, D3 and D5, FU day 28
sTREM-1²	soluble TREM-1	Baseline (pre-dose), D1 to D5: daily, FU day 28
RNA profiles²	whole leukocyte RNA profiles (by arrays)	Baseline (pre-dose), 1h, 6h, 12h D1, D3 and D5, FU day 28
Plasma sample for retention	A plasma sample for future exploratory analyses will be stored (see section 12.12.3)	Baseline (pre-dose), D1
Blood sample for pharmacogenetic analyses^{2,3}	Single Nucleotide Polymorphisms of TREM-1 pathway-related genes.	Baseline, other timepoints are acceptable

EOI: End of infusion of study drug

1: Site; 2: Centralised; third party laboratory provider; 3: optional with separate informed consent

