8.2 Adaptive Design

This study incorporates the use of an adaptive design. Study specific adaptive features and their limits are described in Table 3.

Table 3: Adaptive Protocol Features.

Adaptive study design areas	Features	Limits
Repetition of cohorts	
 Cohorts in stage 1 can be repeated in order to obtain more safety and PK data 	
 Each cohort in stage 1 can be repeated only once The randomisation will follow the originally planned system
Dose levels	
 Dose levels in stage 2 of the study can be dropped or adjusted in accordance with PK, safety and tolerability data collected up to the decision-making point 	
 The maximum dose will not exceed 5.0 mg/kg for the loading dose and 3.0 mg/kg/h for the maintenance dose If a dose level is dropped, the planned number of patients may be reassigned to the remaining dose levels.
Samples and assessments	
 Timing of PK and/or biomarker samples may be adjusted in accordance with evolving data and dosing schedule. Additional or less PK and/or biomarker samples may be taken in accordance with evolving data and dosing schedule. Biomarker measurements may be added or removed in accordance with evolving data and dosing schedule (e.g. mTREM-1) 	
 Minimum: sufficient PK samples according to the respective study objective Study specific maximum blood volume will not be exceeded (see section 12.12.8).
Time Window between onset of shock and initiation of treatment	
 The time window of 24 hours between onset of shock and start of study drug infusion may be shortened for stage 2 in accordance with evolving feasibility data from stage 1 	
 The allowed time window in stage 2 will not be shorter than 12 hours

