15.1 Statistical Methods

15.1.1 General Considerations

The analysis will be computed with SAS Version 9.4 (Copyright© 2013 by SAS Institute Inc., Cary, NC, USA).

Unless otherwise specified, baseline is defined as the last planned assessment prior to first dosing and no subgroup analysis is currently planned.

Missing safety, pharmacodynamic, pharmacokinetic and clinical data will not be replaced and will be treated as missing from summary and statistical analyses.

Unless otherwise specified, all treatment comparisons will be two-sided and significance will be assessed at the 5% level.

All safety, pharmacokinetic, pharmacodynamic and clinical data will be summarised by treatment group (Placebo, Dose level 1, Dose level 2 and Dose level 3), and visit, as appropriate.

Qualitative variables will be presented using the number of patients, the number of missing values, the frequency and the percentage per modality.

Quantitative variables will be reported using the number of patients, the number of missing values, the mean, the standard deviation, the median, the first and the third quartiles, the minimum and the maximum.

Between groups comparisons are calculated using an independent t-test or ANOVA-test for quantitative variables with a parametric distribution, or Mann-Whitney test or Kruskal Wallis-test for variables with a non-parametric distribution.

Data is tested for normality using Kolmogorov-Smirnov-test.

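### Section 11.3.3 can be read as ending D1–D5 biomarker sampling at an outcome-driven end of infusion, against Table 2's fixed days, and the protocol states no window for the biomarker AUC it compares between arms

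*Combined protocol and SAP*

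**What the plan says.** - **End of infusion (11.3.3).** Infusion runs until 12 (± 2) hours after vasopressor withdrawal, to a maximum of 120 (± 2) hours. A list of end-of-infusion assessments follows, including biomarkers and RNA profile. For earlier stops: "If the treatment is stopped any day before D5, the assessments listed above will be performed only once the day of the end of infusion".
- **SOFA exception (11.3.3).** The text continues: "For all patients alive, the SOFA score will however be calculated until day 5, no matter when the study treatment stopped". These extra SOFA values are retrospective: "This data will be collected to the extent available in source data and analysed post-hoc".
- **Schedule (Table 2).** sTREM-1: "Baseline (pre-dose), D1 to D5: daily, FU day 28". Cytokines and endothelial markers: "Baseline (pre-dose), D1, D3 and D5, FU day 28". Neither entry depends on infusion status.
- **Permitted changes (Table 3).** "Timing of PK and/or biomarker samples may be adjusted in accordance with evolving data and dosing schedule". The protocol text records no such change.
- **Analysis.** Biomarker profiles and AUC are secondary PD variables (15.1.3), with no AUC window given. PD endpoints are compared by ANOVA on logs, each dose against placebo at the two-sided 10% level (15.1.5), and no baseline term is mentioned. One post-baseline sample admits a patient to the PD set (15.1.2). "Missing safety, pharmacodynamic, pharmacokinetic and clinical data will not be replaced and will be treated as missing" (15.1.1). The synopsis names a repeated-measures mixed model for cytokines and vital signs. Sections 15 and 15.1.3 leave further detail to a separate SAP.

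**The concern.** Vasopressor use and time to shock reversal are study endpoints, so the event that ends infusion is one the drug is hoped to bring forward. If D1–D5 sampling ends with infusion, patients who recover sooner have a shorter observation window. An AUC over that window is smaller simply because less time is integrated, and an arm with faster shock reversal would appear to have a suppressed marker.

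The dose/PD relationship is a secondary objective (section 7) and the data are meant to help design later studies (8.5.1). A lower AUC could therefore be taken as target engagement when it reflects only shorter infusion. With missing values not replaced and no window stated, nothing in the protocol text rules this out.

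**Working it through.** **1. Arm sizes.** Each dose has 3 (stage 1) + 9 (stage 2) = 12 patients; placebo has 3 × 1 + 9 = 12; total 4 × 12 = 48, as stated in 15.2. The protocol gives no shock duration, marker time course or marker variance, so every input below is an assumption.

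**2. Effect of the window alone.** For a marker declining exponentially with half-life h days and infusion ending on day e, AUC(0–e)/AUC(0–5) = (1 − 2^(−e/h)) / (1 − 2^(−5/h)).
- e = 2, h = 2: (1 − 0.500)/(1 − 0.177) = 0.61.
- e = 2, h = 1 and 4: 0.77 and 0.51.
- e = 1, h = 1, 2 and 4: 0.52, 0.36 and 0.28.

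Two patients with identical trajectories can thus differ about twofold in AUC.

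**3. Between-arm simulation, no drug effect on the marker.** Two independent simulations used 12 per arm and tested log AUC to end of infusion at the two-sided 10% level.
- *Simulation A:* four-arm pooled variance; lognormal shock duration (log-SD 0.7, placebo median 2–4 days); infusion = shock + 12 h, maximum 5 days; marker flat, or falling with a 3-day half-life to a 20% floor; between-patient log-SD 0.5 or 1.0, residual 0.35; 10,000 trials per setting.
- *Simulation B:* two-arm t-test; marker half-life 2 or 4 days; between-patient log-SD 0.4 or 0.8; shock-duration medians 3 v 3, 3 v 2, 4 v 2 and 3 v 1.5 days; 4,000 trials per setting.

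| Shock in drug arm | A: AUC ratio (rejection) | B: AUC ratio (rejection) |
|---|---|---|
| Same | 0.99–1.01 (10%) | 1.00–1.01 (10–11%) |
| 15% shorter | 0.89–0.94 (10–12%) | not run |
| One-third shorter | 0.76–0.84 (12–22%) | 0.86–0.90 (11–17%) |
| Halved | 0.62–0.73 (17–42%) | 0.76–0.85 (13–30%) |

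The direction agrees; the size depends on the assumed kinetics. In B, AUC over a fixed 0–D5 window with sampling continued held 9.3–10.5%. In A, with one-third to one-half shortening, AUC to D28 gave ratios of 0.99–1.01 (flat marker) or 1.04–1.09 (falling), with rejection of 9–13%.

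**4. Dividing AUC by its duration does not cure it.** For a falling marker the bias reverses: ratios of 1.04–1.09 in A and 1.05–1.16 in B.

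**5. What the alternatives deliver.** In A, the fraction still on infusion at D1 was 98–100% (placebo) and 84–99% (drug). At D3 it was 37–75% and 9–54%. With shortened shock and no marker effect, log change to D1 gave a ratio of 1.00 with 9–11% rejection, and the mixed model at D3/D5 gave ratios of 1.00–1.04.

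Simulated power for a true 40% lower marker from D1 (ratio 0.6; median shock 3 days, unchanged):
- AUC to last infusion-period sample: 20–37%
- baseline-to-D1 AUC: 14–26%
- log change to D1: 79–81%
- mixed model over D1/D3/D5: 82–86%

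With shock also halved, the mixed model had 70–75% and D1 change 79–80%. The simulated mixed model used a common baseline and known variance components, so its figures are somewhat favourable.

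**6. How much of that is baseline correction.** Take |log 0.6| = 0.511, residual SD 0.35, SE = SD × √(2/12), 44 df (critical t 1.68).
- Uncorrected log D1, between-patient SD 0.5: SD = √(0.25 + 0.1225) = 0.610, SE = 0.249, 0.511/0.249 = 2.05, power 65%.
- Uncorrected, between-patient SD 1.0: SD = 1.059, SE = 0.433, ratio 1.18, power 32%.
- Change from baseline: SD = 0.35 × √2 = 0.495, SE = 0.202, ratio 2.53, power 80%.

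Much of the gain therefore comes from using the baseline value. Avoiding the variable window is what removes the bias.

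**The case against.** **The sentence may only forbid duplication.** It could mean that the daily set and the end-of-infusion set are not both done on the same day. The list ties its blood samples to Table 2. It also contains adverse events, mortality and concomitant therapy, which other sections clearly continue after infusion, so it cannot stop everything listed. This stands, and is why the point is put as a possible reading. On the other side, 11.3.2 ties the daily set to the treatment period, and SOFA alone is then exempted by way of contrast. Section 15.5 confirms that later SOFA values were treated as missing in the original analysis, but that is direct evidence for SOFA only.

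**AUC to end of infusion is not an endpoint the protocol states.** Correct. The separate SAP is not in the reviewed text and may set another window; D28 samples are also scheduled, and AUC to D28 is little affected.

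**The largest figures need halved shock.** Correct; at 15% shortening the error rate is essentially nominal.

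**Safeguards exist.** Numbers of patients and of missing values by visit, infusion start and end times, and the cytokine mixed model are already planned, and PD is labelled exploratory. They would help a careful reader see the problem. They do not correct a test on AUC over unequal windows.

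A reader might also infer that the SOFA extension is seriously biased because it has no rule for death. The documents do not support that weight. The extension is post-hoc, has its own SAP, and SOFA is summarised descriptively. Under assumed day-5 mortality of 5–20%, with the drug arm the higher, the survivors-only shift is 0.1–0.3 points, or 0.06–0.21 of its standard error. Ranking death worst is a convention, not a correction that the plan lacks.

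**Conclusion.** The point holds in conditional form. The protocol leaves 11.3.3 and Table 2 unreconciled for biomarkers and states no AUC window. If sampling stops at end of infusion, and if AUC is taken to that point, the planned comparison confuses shorter shock with a lower marker. Error at a nominal 10% is then 10–12% for 15% shorter shock, 11–22% for one-third shorter and 13–42% for halved shock, all under assumed kinetics and variances. There is no bias if shock duration is equal between arms.

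It would go too far to conclude that samples were in fact stopped, or that the reported PD analysis is biased: the text allows another reading and the SAP may fix the window. The primary safety objective is not touched. The point is worth fixing because a better comparison uses samples already scheduled. The difference between patients alive (11.3.3) and surviving patients (15.5) is a minor clarification.

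**What to change.** 1. Reconcile 11.3.3 with Table 2: state whether D1–D5 biomarker samples continue after end of infusion, and clarify ECG and safety laboratory in the same edit.
2. Do not test AUC over windows that depend on infusion length. Compare log marker at D1 between arms, adjusted for log baseline.
3. Analyse D1/D3/D5 (daily for sTREM-1) with the mixed model already named for cytokines, with log baseline as covariate, extended to sTREM-1 and the endothelial markers.
4. Show any AUC to end of infusion descriptively, beside infusion duration.
5. Do not make baseline-to-D1 AUC the main comparison: it is not baseline-corrected, and half its weight is the pre-dose value.
6. Use one wording for the SOFA population in 11.3.3 and 15.5.

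If the original analysis is complete, as 15.5 suggests, items 2–4 become labelled supplementary analyses.

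**Cost:** SAP wording and programming, with no new patients or samples. D1 alone would miss a late effect, and the mixed model assumes that missing samples are explained by observed values.

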11.3.4 End of Study / Premature withdrawal

An End of Study visit will be performed at 28 ± 2 days after the initiation of MOTREM treatment.

The following assessments will be performed:

- Concomitant therapy
- Weight
- SOFA score
- Vital signs
- ECG
- Vasopressor use
- Invasive mechanical ventilation
- Intubation
- Adverse events
- Blood sample for ABG and P/F
- Mortality
- Serious adverse events
- Blood samples for laboratory tests (according to schedule provided in Table 2)
 - Clinical Laboratory

- Anti-drug antibodies (ADA)
- Biomarkers
- RNA profile
- Direct antibody test (direct Coombs)

In case the patient was discharged already, effort should be made to perform as many assessments as reasonably possible. The reasons for missing values must be documented.

11.3.5 Follow-up Period

A follow-up visit will be performed at 90 ± 2 days after the initiation of MOTREM treatment. A documented phone call to patient or carer is acceptable for this purpose.

The following assessments will be performed:

- Mortality
- Relevant changes to patient's condition

